### 7.2 Study completion and post-study treatment

Each subject will be required to complete the study in its entirety and thereafter no further study treatment will be made available to them. Study completion is defined as when the last subject completes the EoS visit (Visit 777), and any assessments associated with this visit have been documented and followed-up appropriately by the Investigator.

After study participation, the patients will continue to be treated by his/her general practitioner according to the local standard clinical management related to the underlying disease. The investigator must provide follow-up medical care for all subjects who are prematurely withdrawn from the study, or must refer them for appropriate ongoing care.

### **7.2.1 Lost to follow-up**

For subjects whose status is unclear because they fail to appear for study visits without stating an intention to discontinue or withdraw, the investigator should show "due diligence" by documenting in the source documents steps taken to contact the subject, e.g. dates of telephone calls, registered letters, etc. A subject should not be formally considered lost to follow-up until his/her scheduled EoS visit would have occurred.

### **7.3 Withdrawal of consent**

Subjects may voluntarily withdraw consent to participate in the study for any reason at any time.

Withdrawal of consent occurs only when a subject does not want to participate in the study anymore, does not want any further visits or assessments or study related contact and does not allow analysis of already obtained biologic material.

If a subject withdraws consent, the investigator must make every effort to determine the primary reason for this decision and record this information. Study treatment must be discontinued and no further assessments conducted. All biological material that has not been analyzed at the time of withdrawal must not be used. Further attempts to contact the subject are not allowed unless safety findings require communicating or follow-up.

### **7.4 Study stopping rules**

As a guidance, dose limiting toxicities (DLTs) will be assessed according to the standardized toxicity grading scale.

The study will be placed on hold with no further dosing pending full safety review if *any* of the following criteria are met:

- One (1) patient with CFZ533-related death.
- Three (3) or more patients presenting with a serious adverse event that is related to CFZ533.
- One (1) patient presenting with CFZ533-related cytokine release syndrome.
- One (1) patient presenting with a CFZ533-related thromboembolic events that is at least of moderate severity.
- More than one (1) patient with a severe allergic reaction within the first 5 treated subjects or an incidence of >20% thereafter.
- Any treatment-related, severe adverse event considered drug related by the Investigator with the following exceptions:
  - Events not requiring treatment, and diagnostic procedures involving elective or non-urgent hospital admission,

- Disease Specific Events that are due to the patients underlying MG diagnosis,
- AEs/SAEs unrelated to the experimental compound as determined by the Investigator or Novartis.
- Two (2) or more patients presenting with:
  - Acute severe exacerbation of MG symptoms requiring hospitalization for treatment.
  - Progressive renal insufficiency or acute kidney injury defined as a moderate increase in serum creatinine (1.5 X ULN) in the setting of euvolemia at any time during the study related to CFZ53.
  - Emergent hypogammaglobulinemia defined as a reduction in total serum IgG or IgM concentration by 50% or more from baseline.
  - Severe systemic infection or opportunistic infection that requires treatment, e.g., sepsis, urosepsis, mycoses, pneumonia.
- Clinically significant (according to the Investigator), study drug-related persisting changes from baseline in vital signs, ECGs, or relevant persistent changes in laboratory parameters (not due to existing co-morbidities), in more than one (1) patient within the first 5 treated patients or an incidence of >20% thereafter.
- Other clinically significant changes or effects in the opinion of the Investigator or Sponsor that are deemed unsafe to continue dosing.

All blinded safety data, including disease specific events, will be evaluated by the Sponsor and Investigator on an ongoing basis and at scheduled meetings. The study may be put on hold pending further data analysis, if the principal investigator or the Sponsor considers that the number and/or severity of AEs justify discontinuation of the study.

In addition, a DMC will be instituted (see [Section 10.3](#)) with the aim to review safety data regularly (and efficacy data, if required) as outlined in their charter and at ad hoc meetings. The DMC can recommend stopping the entire trial if it is considered unsafe or unethical to continue administering CFZ533.

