12. Have had signs or symptoms of a clinically significant systemic viral, bacterial or fungal infection within 30 days prior to randomization.
13. Any significant concurrent medical condition such as pulmonary, renal or liver disease that, in the opinion of the principal Investigator, could affect the patient's ability to tolerate or complete the study.
14. Evidence of active or latent tuberculosis as assessed by quantiferon testing at screening (PPD is not recommended as immunosuppression may result in false negative result).
15. Positive serology for HIV antibodies, hepatitis B surface antigen or hepatitis C antibodies (confirmed by an appropriate licensed test) at screening.
16. Any of the following abnormal laboratory values at screening:
  - total white blood cell count (WBC) outside the range of 1,500-15,000/mm^3 (1.5-15.0 x 10^9/L)
  - total white blood cell count (WBC) outside the range of 1,500-20,000/mm^3 (1.5-20.0 x 10^9/L), only for patients taking corticosteroids
  - platelets <100,000/mm^3 (<100 x 10^9/L)
  - Hgb <8.0 g/dL
  - lymphocyte count <500/mm^3 (<0.5 X 10^9 / L)
  - neutrophil count <1500/mm^3 (<1.5 X 10^9 / L)
17. Hypoalbuminemia (serum albumin of less than 2.0 g/dL) at screening.
18. Clinical evidence of liver disease or liver injury or any of the following hepatic conditions:
  - known history of alcohol abuse, chronic liver or biliary disease
  - conjugated bilirubin greater than the upper limit of normal (ULN)
  - alkaline phosphatase (ALP) greater than 2 x ULN
  - AST (SGOT), ALT (SGPT) greater than 2 x ULN
  - gamma-glutamyl-transferase (γ -GT) greater than 2 x ULN

19. History of drug or alcohol abuse within the 12 months prior to dosing, or evidence of such abuse as indicated by the laboratory assays conducted during screening.
20. Have donated blood or experienced a loss of blood >500 mL within 4 weeks of study drug infusion.
21. Allergy to murine or human antibodies.
22. Pregnant or nursing (lactating) women, where pregnancy is defined as the state of a female after conception and until the termination of gestation, confirmed by a positive hCG laboratory test.

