## 7 Discontinuation and study completion

### 7.1 Discontinuation of study treatment

Patients may voluntarily discontinue the study treatment for any reason at any time.

The Investigator should discontinue study treatment for a given patient if, on balance, he/she believes that continuation would be detrimental to the subject's well-being.

- Study treatment **must** be discontinued and patients followed up for safety, if possible, if the following occur:
- In case of non-detectable AChR or MuSK autoantibodies for patients enrolled prior to this amendment.
- Significant increase in MG disease activity requiring treatment outside of a clinical trial setting.
- Worsening of MG with severe oropharyngeal or respiratory weakness (MGFA class IVb or V).
- Rescue medication use (IVIg or plasma exchange).
- Pregnancy.
- Severe or life threatening infusion reaction.
- Major worsening of renal function (e.g. >40% increase from baseline creatinine level).
- Acute infection as a severe AE as judged by the investigator.
- Major elevations (>4.0 x ULN) in amylase or lipase or any abnormal signs or symptoms suggesting pancreatic injury.
- Significant changes in standard coagulation parameters, including prothrombin time (PT), activated partial thromboplastin time (aPTT) suggesting an increased risk for hypercoagulability or any sign or symptom of a TE.
- Any other AE or complication where continued dosing of the patient is considered to be placing them at excess risk.
- Patient withdraws consent (when patient must also be withdrawn from the study).

Patients who are withdrawn from the study for any reason will not be replaced.

Study patients who discontinue participation for any reason or who decide they do not wish to participate in the study further should not be considered withdrawn from the study unless they withdraw their consent (see [Section 7.3](#)). Where possible, they should return for their EoS visit assessments (Visit 777). If they fail to return for these assessments for unknown reasons, every effort (e.g. telephone, e-mail, letter) should be made to contact them as specified in [Section 7.2.1](#). Any unresolved AEs will be followed by the investigator until resolution.

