## 9.4 Renal safety monitoring

Renal events are defined as one of the following:

- confirmed (after ≥ 24h) increase in serum creatinine of ≥ 25% compared to baseline during normal hydration status
- new onset (≥1+) proteinuria, hematuria or glucosuria; or as a
- doubling in the urinary albumin-creatinine ratio (ACR) or urinary protein-creatinine ratio (PCR) (if applicable).

The following two categories of abnormalities/adverse events have to be considered during the course of the study:

- serum creatinine triggers that will require follow up and repeat assessments of the abnormal laboratory parameter
- urine dipstick triggers that will require follow up and repeat assessments of the abnormal laboratory parameter

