**Table 9-3 Specific Renal Alert Criteria and Actions**

Renal Event	Actions
Serum creatinine increase 25 – 49% compared to baseline	Confirm 25% increase after 24-48h Follow up within 2-5 days
Serum creatinine increase $\geq$ 50 % compared to baseline	Follow up within 24-48h if possible Consider drug interruption Consider patient hospitalization /specialized treatment
Albumin- or Protein-creatinine ratio increase $\geq$ 2-fold	Confirm value after 24-48h Perform urine microscopy
Albumin-creatinine ratio (ACR) $\geq$ 30 mg/g or $\geq$ 3 mg/mmol; New dipstick proteinuria $\geq$ 1+	Consider drug interruption / discontinuation
Protein-creatinine ratio (PCR) $\geq$ 150 mg/g or $>$ 15 mg/mmol	
New dipstick glucosuria $\geq$ 1+ not due to diabetes	Blood glucose (fasting) Perform serum creatinine, ACR
New dipstick hematuria not due to trauma	Urine sediment microscopy Perform serum creatinine, ACR
Document contributing factors: co-medication, other co-morbid conditions, and additional diagnostic procedures performed in the CRF	
Monitor patient regularly (frequency at investigator's discretion) until one of the following:	
Event resolution: (sCr within 10% of baseline or protein-creatinine ratio within 50% of baseline)	
Event stabilization: sCr level with $\pm$ 10% variability over last 6 months or protein-creatinine ratio stabilization at a new level with $\pm$ 50% variability over last 6 months.	

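### The renal study-hold item in Protocol 7.4 sets a creatinine increase against ULN, while 7.1, 9.4 and Table 9-3 all measure it from the patient's own baseline

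*Protocol*

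**What the plan says.** Protocol 7.4 lists events that suspend dosing pending a full safety review. One group is headed "Two (2) or more patients presenting with", and its renal item reads "Progressive renal insufficiency or acute kidney injury defined as a moderate increase in serum creatinine (1.5 X ULN) in the setting of euvolemia". The item adds that the event must be drug-related and may occur whenever the patient is in the study. The only number is a multiple of ULN. Baseline is not mentioned.

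The other creatinine rules use the patient's own baseline:

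- Section 7.1, among the events for which treatment must be stopped: "Major worsening of renal function (e.g. >40% increase from baseline creatinine level".
- Section 9.4, definition of a renal event, to be confirmed after at least 24 hours: "increase in serum creatinine of ≥ 25% compared to baseline during normal hydration status".
- Table 9-3: bands of 25–49% and of 50% or more. The lower band instructs "Confirm 25% increase after 24-48h". The upper band asks the site to consider interrupting the drug.

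Within the same two-patient group in 7.4, the immunoglobulin item is also tied to baseline: "Emergent hypogammaglobulinemia defined as a reduction in total serum IgG or IgM concentration by 50% or more from baseline".

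On entry, exclusion criterion 13 begins "Any significant concurrent medical condition such as pulmonary, renal or liver disease that, in the opinion of the principal Investigator". It turns on whether the condition would get in the way of tolerating or finishing the study. No criterion in Section 4 gives a numeric creatinine limit. The readable SAP text adds no definition of the renal hold event.

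**The concern.** The hold item is there to detect a renal signal across patients. Because it uses a different reference from every other creatinine rule, the rise it demands depends on where the patient started. A patient with low-normal creatinine must rise a long way before meeting it. A patient who enters above ULN may need only a small rise.

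The adjectives also run the wrong way. For any normal baseline, the increase that 7.4 calls moderate is larger than the one that 7.1 gives as an example of major worsening.

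The two rules also interact. Treatment can be stopped under 7.1 at a rise that does not yet meet the hold item. If creatinine then stabilises or falls, that patient never meets it. Several drug-related cases of this kind could accumulate without the renal criterion being reached.

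**Working it through.** The plan states no operating figure for this rule, so there is nothing to reproduce. The check is threshold arithmetic.

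**Inputs.** Hold level 1.5 × ULN (7.4), read as met at or above that level. Individual-stop example, a rise over 40% (7.1). Renal event, 25% or more (9.4). Upper alert band, 50% or more (Table 9-3). Planned randomisation of 44, with 22 per arm (11.6). Assumption: b = baseline creatinine ÷ ULN, with normal meaning b ≤ 1.0. The documents give no distribution of b, so a range is shown.

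**Formulas.** Level after a 40% rise = 1.4b. Level after a 50% rise = 1.5b. Rise needed to reach the hold level = 1.5/b − 1.

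| b | Level at +40% (× ULN) | Level at +50% (× ULN) | Rise needed for 1.5 × ULN |
|---|---|---|---|
| 0.5 | 0.70 | 0.75 | 200% |
| 0.6 | 0.84 | 0.90 | 150% |
| 0.8 | 1.12 | 1.20 | 88% |
| 1.0 | 1.40 | 1.50 | 50% |
| 1.2 | 1.68 | 1.80 | 25% |
| 1.4 | 1.96 | 2.10 | 7% |

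**Break-even baselines.**

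- A 40% rise reaches the hold level only if b ≥ 1.5/1.4 = 1.07, which is already above normal.
- A 50% rise reaches it only if b ≥ 1.5/1.5 = 1.0. For b below 1.0, a patient in the top band of Table 9-3 may still fall short.
- A 25% rise reaches it if b ≥ 1.5/1.25 = 1.2. Above that, the level can be reached by a rise smaller than the 9.4 renal event.

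**The numeric fallback.** The laboratory-change item in 7.4 applies to clinically significant, drug-related, persisting changes "in more than one (1) patient within the first 5 treated patients or an incidence of >20% thereafter". Once past the first five, and with all planned patients treated, 20% of 44 is 8.8, so 9 patients are needed. If counted on the active arm only, 20% of 22 is 4.4, so 5 are needed. The renal item needs 2.

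**The case against.** The strongest reply is that the sections do different jobs. Section 7.1 protects one patient, 9.4 and Table 9-3 prompt repeat tests and follow-up, and 7.4 suspends the whole study. A study hold that needs more than an individual stop is an ordinary tiered scheme, and nothing in the protocol says that a patient stopped under 7.1 should count toward the hold. This stands in part: the absence of a link is not in itself an error. But the tiers do not keep their order. Below b = 1.07 the 7.1 example comes first; above it the hold level can come first. A deliberate tiering would not normally reverse with baseline.

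Three stronger readings are tempting, and the documents do not support them:

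- *That a patient stopped at a 40% rise cannot contribute to any hold.* The shortfall concerns the renal item alone. Section 7.4 also lists drug-related severe adverse events, three or more patients with related serious events, persisting laboratory changes, and an open item resting on investigator or sponsor opinion. It adds ongoing blinded review by the sponsor and investigator, and a DMC that can recommend stopping. These routes are real but looser. Severe, in 9.1, means preventing normal activities, which a symptom-free creatinine rise may not do. The serious-event route needs three patients and a seriousness criterion. The laboratory route needs the higher count. The rest is discretion.
- *That 40% is a fixed cut-off.* It is introduced as an example and is a floor. A larger rise can meet the hold item: 50% at b = 1.0, or 150% at b = 0.6.
- *That a trivial rise in a patient with high baseline triggers the item automatically.* The item still requires progressive renal insufficiency or acute kidney injury, euvolemia and relatedness. Such patients are also filtered by exclusion 13 and by the documented clinical-significance decision that 8.4.4 requires for out-of-range screening values. Without a numeric limit they may enter, but no figure says how many would.

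A rationale for the ULN level may lie in redacted text or in the DMC charter, neither of which can be seen. That would explain the choice. It would not tell a site how the references fit together.

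**Conclusion.** The inconsistency is real and should be corrected. The renal hold item is the only creatinine rule in the protocol set against ULN, and it describes as an increase something that it measures as a level. For every baseline at or below ULN, a drug-related rise just over the 7.1 example does not meet it. For b below 1.0, a rise in the top band of Table 9-3 may not meet it either. For b above 1.07 the level can be reached before the 7.1 example, subject to the item's clinical and causal conditions.

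The size depends on the unknown distribution of b and on reading the item as a level; the direction holds across the whole normal range. The other hold routes reduce the consequence but do not supply a pre-specified two-patient renal count on the scale used elsewhere. The conclusion is that the sections must be reconciled, not that either reference or any threshold is the right one.

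**What to change.** Amend the protocol so that the renal item in 7.4 states one reference for the creatinine increase, reconciled with 7.1, 9.4 and Table 9-3. State explicitly whether a patient stopped under the 7.1 renal item counts toward the two-patient hold.

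In the same edit, reconcile 7.1 with Table 9-3. The first requires treatment to stop, with a rise over 40% as its example. The second, at 50% or more, only asks the site to consider interruption. The sponsor's clinical and safety team sets any threshold.

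The cost is a short amendment, plus a matching check of the DMC charter. No new data are needed: creatinine is in the chemistry panel (8.4.4) and chemistry is drawn at screening (3.1). The downside is that the renal hold may be reached at a different, possibly lower, absolute creatinine, and so be reviewed more often.

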## 7.5 Early study termination

The study can be terminated at any time for any reason by Novartis. Should this be necessary, subjects should be seen as soon as possible and treated as a prematurely withdrawn subject and complete their EoS visit assessments as per Assessment Schedule ([Table 8-1](#)). The investigator may be informed of additional procedures to be followed in order to ensure that adequate consideration is given to the protection of the subject's interests.

The investigator will be responsible for informing IRBs/IECs of the early termination of the trial.

## **8 Procedures and assessments**

Visits should be scheduled within the allowed visit/assessment window as specified in the Assessment Schedule ([Table 8-1](#)).

PK samples should be taken at the time points as specified in the Assessment Schedule. When other assessments are scheduled to be performed at the same time-point, these will be taken after the PK samples.

The preferred sequence of data collection during study visits is safety, ECG, followed by vital signs and blood sampling.

## **8.1 Informed consent procedures**

Eligible subjects may only be included in the study after providing written (witnessed, where required by law or regulation), IRB/IEC-approved informed consent.

If incapable of doing so, in cases where the subject's representative gives consent, the subject should be informed about the study to the extent possible given his/her understanding. If the subject is capable of doing so, he/she should indicate assent by personally signing and dating the written informed consent document or a separate assent form.

Informed consent must be obtained before conducting any study-specific procedures (i.e. all of the procedures described in the protocol). The process of obtaining informed consent should be documented in the subject source documents.

The date of signing of informed consent (and withdrawal, if later withdrawn) should be documented in the CRF.

Novartis will provide to investigators a proposed informed consent form that complies with the ICH GCP guideline and regulatory requirements and is considered appropriate for this study. Any changes to the proposed consent form suggested by the investigator must be agreed to by Novartis before submission to the IRB/IEC.

Corporate Confidential Information

In the event that Novartis wants to perform testing on the samples that are not described in this protocol, additional Institutional Review Board and/or Ethics Committee approval will be obtained.

## **8.2 Subject demographics/other baseline characteristics**

Subject demographic and baseline characteristic data to be collected on all subjects include: date of birth, age, sex, race, predominant ethnicity.

Relevant medical history/current medical conditions data includes data prior to signature of informed consent. Where possible, diagnoses and not symptoms should be recorded.

The date of original diagnosis of Myasthenia Gravis and the MG class will be recorded in the CRF.

Medical history of MG and the autoantibodies diagnostic test results (performed at V1) will be maintained/recorded in the source data.

## **Hepatitis screen, HIV screen**

All subjects will be screened for Hepatitis B surface antigen (HBsAg). Screening for Hepatitis C will be based on HCV antibodies.

Evaluation for HIV seropositivity will be performed, and if positive, confirmation by a second technique available at the laboratory site, e.g., Western blot. Appropriate subject counseling will be made available by the Investigator in the event of a positive finding. Notification of state and federal authorities, as required by law, will be the responsibility of the Investigator.

Results will be available as source data and will not be recorded within the eCRF.

## **Alcohol test, Drug screen**

Subjects will be tested for substances of abuse (e.g., alcohol, amphetamines, barbiturates, benzodiazepines, cannabinoids, cocaine, and opiates).

Results will be available as source data and will not be recorded within the eCRF.

